#### **Covariates**

For our main cohort analysis objective #1-2 and #5-8, we will take the following potential confounders into account: age (using birth cohort), sex, region of residency, calendar time of last mutual vaccine dose (i.e., either third or fourth dose depending on boosted vs unboosted- [i.e., 4 vs 3-] or between boosters- [i.e., 4 vs 4-] analyses), vaccination priority group (nursing home residents, healthcare personnel, at risk of severe Covid-19 due to comorbidities), previous SARS-CoV-2 infection and selected comorbidities. For the Covid-19 hospitalised cohort analysis (objective #3), we will also include length of hospitalisation as a covariate (as a proxy for severity of event) but not use previous SARS-CoV-2 infection history (as per eligibility criteria, all included are SARS-CoV-2 infected [as hospitalised due to this infection] and any previous SARS-CoV-2 infection is most likely not a strong confounder within the comparison). For the immunocompromised cohort analysis (objective #4), we will also include subtype of immunocompromised condition (as categorized in the 6 levels in the table above). In addition, we will assess the data distribution to help find the optimal categorization of the variables "Time since SARS-CoV-2 infection", "Time between primary course and first booster", and "Time between first and second booster". Further details of covariate definitions are provided in table below.

Variable	Country	Data source and details	Values/codes
Ago	Denmark	The Civil Registration System. Recorded birth year. Age defined as the country-specific start date minus birth year.	Categorical (for adjustment, using birth year): 5-year bins
Age	Finland	The Finnish Population Information System. Recorded birth year. Age defined as the country-specific start date minus birth year.	Binary (for stratification): ≥ 70 years</td

Variable	Country	Data source and details	Values/codes	
	Norway	Norwegian Population Register. Recorded birth year. Age defined as the country-specific start date minus birth year.		
Sweden		The Total Population Register. Recorded birth year. Age defined as the country-specific start date minus birth year.		
	Denmark	The Civil Registration System. Defined as registered sex.		
Sex	Finland	The Finnish Population Information System. Defined as registered sex.	Binary: male, female	
Jex	Norway	Norwegian Population Register. Defined as registered sex.	billary. maie, lemaie	
	Sweden	The Total Population Register. Defined as registered sex.		
	Denmark	The Danish Vaccination Register. Defined by the date where the respective vaccine dose examined was administered (i.e., third or fourth dose).		
Calendar time period of last	Finland	The National Vaccination Register. Defined by the date where the respective vaccine dose examined was administered (i.e., third or fourth dose).	Categorical (monthly [up to 33 levels]): 1 (27 December 2020-31 January 2021) to month 33 (September 2023)	
mutual vaccine dose a	Norway	The Norwegian Immunisation Register (SYSVAK).  Defined by the date where the respective vaccine dose examined was administered (i.e., third or fourth dose).		
	Sweden	The National Vaccination Register. Defined by the date where the respective vaccine dose examined was administered i.e., third or fourth dose).		
	Denmark	The Civil Registration System. Defined by last known address at the country-specific start date for the rollout of the fourth vaccine dose.		
Dogion of	Finland	The Finnish Population Information System. Defined by last known municipality of residence.	Categorical: Denmark, 5 levels;	
Region of residency	Norway	Norwegian Population Register. Defined by last known address at the country-specific start date for the rollout of the fourth vaccine dose.	Finland, 5 levels; Norway, 5 levels; Sweden, 9 levels	
	Sweden	The Total Population Register. Defined by last known address at the country-specific start date for the rollout of the fourth vaccine dose.		
Covid-19 vaccine priority groups b	Denmark	The Danish Vaccination Register. Defined as governmentally assigned Covid-19 vaccine priority groups, prioritised according to the risk of severe Covid-19 as well as whether being health and social care workers (last update 24 May 2021).	Categorical (3 levels): Severe Covid-19 risk group, healthcare personnel, others	

Variable	Country	Data source and details	Values/codes
	Finland	Register of Social Assistance. Severe Covid-19 risk group was defined as vulnerable individuals in 24-hours care (binary status per 27 December 2021).	
		Social and Healthcare Professionals Register. Healthcare personnel defined as individuals with the right to act as health care personnel as of 27 December 2021.	
	Norway	The Norwegian Information System for the Nursing and Care Sector. Severe Covid-19 risk group was defined as vulnerable individuals being residents at nursing homes (binary status per 27 December 2020).	
		State register of employers and employees. Healthcare personnel defined as binary status per 27 December 2020.	
	Sweden	Register on persons in nursing homes. Severe Covid-19 risk group was defined as vulnerable individuals being residents at nursing homes (binary status as of 31 December 2020)	
	Sweden	The Longitudinal integrated database for health insurance and labour market studies. Healthcare personnel defined as healthcare worker occupation status as of 31 October 2018 (binary).	
	Denmark	The National Patient Register. Defined as primary diagnoses regardless of type of hospital contact registered before the start date for the country-specific rollout of the fourth vaccine dose (look-back 3 years).	Binary: yes/no (ICD-10 codes: J40- J47, J60-J67, J684, J701, J703, J841, J920, J961, J982, J983)
Comorbidity 1:	Finland	Care register for Health Care. Defined as primary or secondary diagnoses before 27 December 2020 (lookback 6 years).	Binary: yes/no (ICD-10 codes: J41- J44, J47)
pulmonary disease	Norway	Norwegian Patient Register. Defined as any recorded ICD-10 diagnosis during inpatient or outpatient contact in hospital or from private-practicing specialists and before first Covid-19 vaccination (look-back 3 years).	Binary: yes/no (ICD-10 codes: E84, J41-J47, J701, J703, J84, J98)
	Sweden	National Patient Register. Defined as any recorded ICD-10 diagnosis during inpatient or outpatient contact and before first Covid-19 vaccination (look-back 3 years).	Binary: yes/no (ICD-10 codes: E84, J41-J47, J84, J98)
Comorbidity 2: Cardiovascular conditions and diabetes	Denmark	The National Patient Register. Defined as primary diagnoses regardless of type of hospital contact registered before the start date for the country-specific rollout of the fourth vaccine dose (look-back 3 years).	Binary: yes/no (ICD-10 codes: E10- E11, I110, I130, I132, I20-I23, I420, I426-I429, I48, I500-I503, I508, I509)
	Finland	Care register for Health Care, Register of Primary Health Care Visits, Special Reimbursement Register and Prescription Centre database. Defined as primary or secondary diagnoses (look-back 6 years) or drug	Binary: yes/no (ICD-10 codes: E10, E11, E13-E14, I11-I13, I15, I20- I25; ICPC-2 codes: T89, T90; ATC codes: A10A, A10B)

Variable Country		Data source and details	Values/codes	
		prescriptions (look-back 3 years) before 27 December 2020.		
	Norway	Norwegian Patient Register. Defined as any recorded ICD-10 diagnosis during inpatient or outpatient contact in hospital or from private-practicing specialists and before first Covid-19 vaccination (look-back 3 years).	Binary: yes/no (ICD-10 codes: E10- E14, I05-I09, I110, I130, I132, I1420, I20-I23, I25-I28, I33-I39, I426-I429, I48, I50)	
	Sweden	National Patient Register. Defined as any recorded ICD-10 diagnosis during inpatient or outpatient contact and before first Covid-19 vaccination (look-back 3 years).  Swedish Prescribed Drug Register. Antidiabetic drugs use defined as ≥2 filled prescriptions during 2020.	Binary: yes/no (ICD-10 codes: E10- E14, I05-I09, I110, I20-I28, I34-I37, I39, I42, I43, I46, I48-I50; ATC code: A10)	
Comorbidity 3: Autoimmunity- related conditions c	Denmark	The National Patient Register. Defined as primary diagnoses regardless of type of hospital contact registered before the start date for the country-specific rollout of the fourth vaccine dose (look-back 3 years).	Binary: yes/no (ICD-10 codes: D510, D590, D591, D690, D693, D86, E050, E063, E271, E272, G122G, G35, G610, G700, I00, I01, K50, K51, K743, K900, L12, L40, L52, L80, L93, M05, M06, M08, M300, M313, M315, M316, M32, M33, M34, M35, M45)	
	Finland	Care register for Health Care, Special Reimbursement Register and Prescription Centre database. Defined as primary or secondary diagnoses (look-back 6 years) or drug prescriptions (look-back 3 years) before 27 December 2020.  *Only if patient also used one of the listed drugs (marked with **)  **Only if patient also had one of the diagnoses (marked with *)	Binary: yes/no (ICD-10 codes: D7081, D7089, D80-D84, E250, E271, E272, E274, E310, E896, D86*, K50*, K51*, L40*, M02*, M05-M07*, M139*, M45*, M460*, M461*, M469*, M941*; ATC-codes**: H02AB02, H02AB04, H02AB06, H02AB07, L01BA01, L01XC02, L04AA06, L04AA10, L04AA13, L04AA18, L04AA24, L04AA26, L04AA29, L04AA33, L04AA37, L04AB, L04AC, L04AA01, L04AD02, L04AX01, L04AX03)	
	Norway	Norwegian Patient Register. Defined as any recorded ICD-10 diagnosis during inpatient or outpatient contact in hospital or from private-practicing specialists and before first Covid-19 vaccination (look-back 3 years).	Binary: yes/no (ICD-10 codes: G35, K50-K51, M05-M09, M13-M14)	
	Sweden	National Patient Register. Defined as any recorded ICD-10 diagnosis during inpatient or outpatient contact and before first Covid-19 vaccination (look-back 3 years).	Binary: yes/no (ICD-10 codes: D86, G35, K50, K51, L40, M05-M09, M13, M14, M45)	
Comorbidity 4: Cancer	Denmark	The National Patient Register. Defined as primary diagnoses regardless of type of hospital contact registered before the start date for the country-specific rollout of the fourth vaccine dose (look-back 3 years).	Binary: yes/no (ICD-10 codes: C00–C85 (without C44), C88, C90-C96)	

Variable	Country	Data source and details	Values/codes	
	Finland	Care register for Health Care and Special Reimbursement Register. Defined as primary or secondary diagnoses before 27 December 2020 (look-back 6 years).	Binary: yes/no (ICD-10 codes: C00– C97 (without C44), D051, D39)	
	Norway		Binary: yes/no (ICD-10 codes: C00-C96 (without C44))	
	Sweden	National Patient Register. Defined as any recorded ICD-10 diagnosis during inpatient or outpatient contact and before first Covid-19 vaccination (look-back 3 years).	Binary: yes/no (ICD-10 codes: C00-C96 (without C44), D45-D47)	
	Denmark	The National Patient Register. Defined as primary diagnoses regardless of type of hospital contact registered before the start date for the country-specific rollout of the fourth vaccine dose (look-back 3 years).	Binary: yes/no (ICD-10 codes: I12, I13, N00-N05, N07, N11, N14, N17-N19, Q61)	
Comorbidity 5: Moderate to	Finland	Care register for Health Care. Defined as primary or secondary diagnoses before 27 December 2020 (lookback 6 years).	Binary: yes/no (ICD-10 codes: I12, I13, N00-N05, N07, N08, N11, N14, N18, N19, E102, E112, E142)	
severe renal disease	Norway	Norwegian Patient Register. Defined as any recorded ICD-10 diagnosis during inpatient or outpatient contact in hospital or from private-practicing specialists and before first Covid-19 vaccination (look-back 3 years).	Binary: yes/no (ICD-10 codes: I12- I13, N00-N05, N07, N11, N14, N17- N19, Q61)	
	Sweden	National Patient Register. Defined as any recorded ICD-10 diagnosis during inpatient or outpatient contact and before first Covid-19 vaccination (look-back 3 years).	Binary: yes/no (ICD-10 codes: I12, I13, N00-N05, N07, N11, N14, N17-N19, Q61)	
	Denmark	The Danish Microbiology Database. Defined as the date of any (last) registered positive PCR test for SARS-CoV-2 prior to the start date for the country-specific rollout of the fourth vaccine dose.		

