#### 7. RATIONALE AND BACKGROUND

The emergence of the SARS-CoV-2 Omicron variant in late 2021 quickly raised concerns about the effectiveness of the original monovalent Covid-19 vaccines. Bivalent booster vaccinations, which incorporated components from both the ancestral strain and the Omicron variant, were developed to improve protection against the new predominant variant. Subsequently, bivalent boosters were introduced in many countries, including the Nordic countries during autumn 2022 as a 4th dose to the general adult population (and as any additional booster for immunocompromised individuals) and results from a number of studies evaluating the effectiveness of bivalent booster vaccinations in different populations and settings are now available.

The protection afforded by the bivalent boosters against SARS-CoV-2 infection appears to be modest.(2-4) In the United States, Link-Gelles and colleagues investigated the comparative effectiveness of bivalent mRNA booster doses against symptomatic SARS-CoV-2 infection in individuals who had previously received monovalent vaccines only.(2) The study found that a bivalent mRNA booster dose provided additional protection against symptomatic XBB/XBB.1.5 infection for at least the first three months after vaccination in individuals who had previously received 2-4 monovalent vaccine doses. Vaccine effectiveness was 52% against symptomatic BA.5 infection and 48% against symptomatic XBB/XBB.1.5 infection in persons aged 18-49 years. A cohort study conducted in the Netherlands by Huiberts and colleagues, assessed the comparative effectiveness of bivalent BA.1 vaccination against self-reported Omicron SARS-CoV-2 infection.(3) The study involved 32,542 participants who had previously received primary and one or two monovalent booster Covid-19 vaccinations. The results showed 31% effectiveness in 18-59-year-olds and 14% effectiveness in 60-85-year-olds, indicating that a bivalent booster provided little additional benefit in preventing SARS-CoV-2 infection. A study in Qatar evaluated the comparative effectiveness of the bivalent mRNA-1273.214 vaccine against SARS-CoV-2 infection in individuals aged 12 and older.(4) The study reported a modest protection of 24.7% against infection with the bivalent vaccine in a period dominated by the Omicron XBB subvariants. The protection was 16.4% among persons with no prior infection and 35.3% among persons with prior infection.

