## **Primary objectives:**

1. To provide estimates of VE against severe Covid-19 outcomes at day 365 after immunisation with a BA.1 or BA.4-5 bivalent booster as a fourth dose, comparing a) the BA.1 and BA.4-5 bivalent booster against not having received a fourth dose and b) between the BA.1 and BA.4-5 bivalent and the original monovalent booster.

- 2. To provide estimates of waning of VE against severe Covid-19 outcomes as the three-monthly relative reduction in vaccine effectiveness until day 365 after immunisation with a BA.1 or BA.4-5 bivalent booster as a fourth dose, comparing a) the BA.1 and BA.4-5 bivalent booster against not having received a fourth dose and b) between the BA.1 and BA.4-5 bivalent and the original monovalent booster.
- 3. To provide estimates of VE against all-cause mortality at 3, 6, and 9 months post discharge for COVID-19 hospitalisation, comparing a) individuals who received BA.1 and BA.4-5 bivalent boosters as fourth dose against individuals not having received a fourth dose and b) individuals who received the BA.1, BA.4-5 bivalent, or original monovalent boosters.

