## 9.7 Data analysis

#### **Procedures**

[figure not shown]
We will use a matched study design to evaluate the effectiveness of a bivalent BA.1 or BA.4-5 (or monovalent [original]) mRNA-booster vaccine (as the fourth dose) in comparison with having received three monovalent vaccine doses only (i.e., nonboosted with a fourth dose) as well as between fourth dose recipients. For the boosted vs nonboosted (i.e., 4 vs 3 dose) comparisons, individuals who have received a fourth dose will be matched on the day of vaccination with individuals who have not yet received a fourth dose. Individuals will be matched on age (5-year bins), calendar time according to when the third dose was received (monthly bins), and a propensity score including sex, region of residence, vaccination priority groups (i.e., individuals at high-risk of severe Covid-19 or healthcare workers), selected comorbidities (chronic pulmonary disease, cardiovascular conditions or diabetes, autoimmunity-related conditions, cancer, and moderate to severe renal disease), and previous history of SARS-CoV-2 infection characteristics. The day the fourth dose was administered within each matched pair will serve as the index date for both individuals. If individuals who were included as a

matched nonboosted (previously three-dose vaccinated) individual (i.e., a reference individual) received a fourth dose later than the assigned index date, they will be allowed to potentially re-enter as a fourth-dose recipient in a new matched pair on that given date. The figure below illustrates the study cohort construction.

For the between booster (i.e., 4 vs 4 dose) comparison, BA.4-5 booster and BA.1 booster recipients (as a fourth dose) will be matched on age (5-year bins), calendar time according to when the fourth dose was received (monthly bins), and a propensity score including sex, region of residence, vaccination priority groups (i.e., individuals at high-risk of severe Covid-19 or healthcare workers), selected comorbidities (chronic pulmonary disease, cardiovascular conditions or diabetes, autoimmunity-related conditions, cancer, and moderate to severe renal disease), and previous history of SARS-CoV-2

infection. The day the fourth dose was administered will serve as the index date for each respective individual. The figure below illustrates the study cohort construction.

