We will examine risk of all-cause mortality at 3, 6, and 9 months since recovery from first Covid-19 hospitalisation. The source population for this cohort will be the same as the main cohort for the main comparative analyses (i.e., individuals aged ≥50 years who have received at least 3 doses of vaccine and no previous Covid-19 hospitalisation prior to study start). Recovery will be defined as discharge from an inpatient hospital stay for Covid-19 (i.e., similar to the outcome definition used in the main analyses). We will start follow-up on day 8\* since discharge, to ensure that there are no rapid rehospitalisations (if this occurs, the individual, can re-enter the cohort on day 8\* after discharge from the re-hospitalisation) and end follow-up on outcome event of all-cause mortality; emigration; Covid-19 vaccination; day 90, 180, or 270; or end of study period. Since this is likely to be a cohort of limited size, we will utilize a complete cohort analysis using multivariate Cox regression model with covariate adjustment (same covariates as main analyses, except not previous SARS-CoV-2 infection, and including length of hospitalization). The exposure (Covid-19 vaccination status [4 vs 3 doses]) will be evaluated at time of Covid-19 hospitalisation (admission date). Dependent on data availability we will consider further categorization of the associations according to subgroups similar to those of the main cohort analyses.

\*Day 8 is a prespecified arbitrary best guess. The final grace period will be determined by examining the distribution of days after discharge for any rehospitalisations in the Danish data. Depending on the data distribution, we will decide if it is necessary to perform additional sensitivity analysis in this regard.

*Immunocompromised (objective #4)* 

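### Objective 3 leaves prior SARS-CoV-2 infection out of its Cox model for one invalid and one unsupported reason, although the variable is already defined at baseline in all four countries

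*Protocol*

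**What the plan says.** Protocol section 8 lists objective 3 among the primary objectives: "To provide estimates of VE against all-cause mortality at 3, 6, and 9 months post discharge for COVID-19 hospitalisation". Section 9.7 analyses it in the complete hospitalised cohort with a Cox model and no matching. The adjustment set there is "same covariates as main analyses, except not previous SARS-CoV-2 infection, and including length of hospitalization".

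The Covariates text in 9.3 agrees. For this cohort the protocol will add length of stay "but not use previous SARS-CoV-2 infection history". Two reasons share one bracket. The first is that "all included are SARS-CoV-2 infected [as hospitalised due to this infection". The second is that "any previous SARS-CoV-2 infection is most likely not a strong confounder within the comparison".

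Elsewhere the variable is kept. The same Covariates text lists previous infection among the potential confounders for objectives 1-2 and 5-8. For boosted versus nonboosted, the propensity score in 9.7 includes "previous history of SARS-CoV-2 infection characteristics", and the between-booster score also includes infection history. Objective 4 uses the same matched approach. The covariate table gives a source in each of the four countries. The Danish entry reads "Defined as the date of any (last) registered positive PCR test for SARS-CoV-2 prior to the start date" of the fourth-dose rollout, and the other three are equivalent.

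**The concern.** The first reason does not support the omission. That all patients share the infection that led to admission does not make them alike in earlier infection. Section 9.2 excludes only people with a Covid-19 hospitalisation before the country start date. People with an earlier infection that did not lead to admission stay in, alongside people with none registered.

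The second reason addresses the right question but is not backed by anything in the document. Earlier infection could plausibly influence both whether someone took a fourth dose and how they fared after admission.

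Objective 3 is the only objective that drops the variable. It is also unmatched, so the Cox covariates are its only control of confounding. What is at stake is avoidable confounding of a primary mortality contrast.

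**Working it through.** **Inputs.** The protocol gives no effect size, event count, prevalence of earlier infection by dose group, or mortality effect of earlier infection for objective 3, so there is no stated figure to reproduce. The only usable number is in 9.5: at least 2,250 hospitalised people with four doses. Everything else below is assumed.

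**Step 1: size of the omitted-covariate effect.** Let p4 and p3 be the shares with earlier infection among four- and three-dose patients, and g the mortality hazard ratio for earlier infection. Treating it as one binary covariate not captured by the others, with deaths not too common, approximately:

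observed HR / true HR = [1 − p4(1 − g)] / [1 − p3(1 − g)]

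With p4 of 15-20%, p3 of 30-40% and g of 0.5-0.8:
- Smallest (p4 = 0.20, p3 = 0.30, g = 0.8): 0.96 / 0.94 = 1.02.
- Largest (p4 = 0.15, p3 = 0.40, g = 0.5): 0.925 / 0.80 = 1.16.

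A true hazard ratio of 0.70 would be seen as 0.71 to 0.81.

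**Step 2: direction.** If the two prevalences are swapped, the factors invert to about 0.86 to 0.98. If earlier infection marks higher mortality (g = 1.5, p4 = 0.20, p3 = 0.40), the factor is 1.10 / 1.20 = 0.92. With equal prevalence, or g = 1, it is exactly 1.

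**Step 3: restriction to admitted patients.** Even if booster and earlier infection were unrelated in the source cohort, they become associated among the admitted if booster protection against admission differs by earlier infection. Section 7 reports such a difference in a cited study, for infection rather than admission: "The protection was 16.4% among persons with no prior infection and 35.3% among persons with prior infection". Assume 30% earlier infection in both groups, a risk ratio of 0.4 for admission with earlier infection, and g = 0.6:
- Three doses: 0.30 × 0.4 / (0.30 × 0.4 + 0.70) = 0.12 / 0.82 = 14.6% with earlier infection.
- Four doses, using the section 7 protections: 0.12 × 0.647 / (0.12 × 0.647 + 0.70 × 0.836) = 11.7%.
- Factor: (1 − 0.4 × 0.117) / (1 − 0.4 × 0.146) = 1.01.

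An opposite and larger contrast, 65% protection without and 30% with earlier infection, has no support in the protocol. It gives 0.084 / (0.084 + 0.245) = 25.5% in four-dose patients and a factor of 0.95.

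**Step 4: scale against precision.** Assume as many three-dose as four-dose patients (2,250 each) and 5%, 10% or 20% mortality, so 225, 450 or 900 deaths. With SE(log HR) = 1/√(deaths × 0.25), the 95% interval extends by a factor of about 1.30, 1.20 or 1.14 either side. The largest factor in step 1, 1.16, exceeds only the last of these.

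**Step 5: timing.** Section 9.2 excludes anyone whose fourth dose preceded the country start date. The existing variable stops at that date, so it cannot be a consequence of an eligible fourth dose.

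**The case against.** The strongest reply is that the omission is deliberate, disclosed and stated the same way in 9.3 and 9.7, and that the second reason separates earlier infection from the current one. That is correct. A reader might infer that the protocol simply confuses the two infections. That fits the first reason only, and nothing here is a contradiction between sections.

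A second reply is that confounding has not been shown. Prior infection is called a potential confounder for Covid-19 hospitalisation and death in the general cohort. Objective 3 has a different outcome, all-cause death from day 8 after discharge, in a different population. This also stands. A reader might infer that the mortality contrast is biased, but every input above is assumed, and much of the range is compatible with a weak confounder. The protocol's judgement is unsupported, not refuted.

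A third tempting step is to say that restriction to admitted patients makes matters materially worse, citing section 7. The document does not support that. The study cited there found higher, not lower, protection with prior infection, and its figures give a factor of only about 1.01.

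Finally, 9.9 says there is no information on at-home antigen tests, so adjustment would be incomplete. That limits the gain but is no reason to omit the variable, which the protocol uses elsewhere with the same weakness. Section 9.7 says subgroups like those of the main analyses may be considered, depending on data availability. That does not commit the sponsor to any adjusted analysis.

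**Conclusion.** The point holds in moderate form. A baseline variable that precedes exposure, is defined in all four countries and is adjusted for in the main-cohort analyses is left out of a primary, unmatched analysis. One reason given is invalid and the other unsupported. The hazard ratio may carry avoidable confounding, by a factor of 1.02 to 1.16 under the assumed prevalences (15-20% versus 30-40%) and mortality hazard ratio (0.5-0.8). Other equally admissible assumptions put the factor at or below 1. The effect is small to moderate over most of this range and approaches the width of the confidence interval only with strong imbalance and a strong effect. It should be corrected because correction is cheap, not because the analysis is shown to be wrong.

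**What to change.** In the Covariates text of 9.3 and the objective 3 paragraph of 9.7, keep previous SARS-CoV-2 infection in the Cox model. Use the definition already in the covariate table: last registered positive PCR before the country-specific start date. Add an explicit level for none registered, since the table lists only three time-since-infection categories. Delete the rationale that all included patients are infected.

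Do not widen the definition to any positive test before the admission episode. That would admit infections after the fourth dose, which the booster can affect. Section 9.9 already declines to study infection following vaccination because of collider bias.

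The cost is a wording change in two places and two to three extra model parameters, against at least 2,250 four-dose admissions expected. Control remains partial: unregistered infections, and those between the start date and the admission episode, are not captured.
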